6.2 Timing of Evaluations

6.2.1 Screening Evaluations

Screening evaluations must occur prior to the participant starting any study medications, treatments, or interventions.

Screening and study entry visit evaluations may be combined unless not allowed per the relevant appendix/appendices. If feasible, screening evaluations may occur remotely.

Study entry visit evaluations must be done prior to administration of study agent.

6.2.2 Entry Evaluations

Entry evaluations must occur ≤48 hours after screening evaluations unless otherwise specified.

Participants must be expected to begin study treatment no more than 7 days from self-reported onset of COVID-19 related symptoms or measured fever as noted in [section 4.1.1.4](#).

6.2.3 Post-Entry Evaluations

On-Treatment/Post-Treatment Evaluations

Evaluations should occur in the visit windows described in [Tables 6.1-1](#) and [6.1-2](#).

Study Completion Evaluations

Participants will be evaluated at week 24 or later, depending on the agent-specific appendix.

6.2.4 Event-Driven Evaluations

See relevant appendix/appendices for details of any event-driven evaluations.

6.2.5 Discontinuation Evaluations

Evaluations for Randomized Participants Who Do Not Start Investigational Agent/Placebo

All eCRFs must be keyed for the period up to and including the entry visit. Participants who were randomized but do not start investigational agent or placebo will be prematurely discontinued from the study and will not be followed.

Premature Treatment Discontinuation Evaluations

Participants who discontinue investigational agent or placebo early should remain on study and all evaluations should be performed as outlined in [Tables 6.1-1](#) and [6.1-2](#).

Premature Study Discontinuation Evaluations

Participants who discontinue study participation should have premature study discontinuation evaluations, as outlined in [Tables 6.1-1](#) and [6.1-2](#) and the relevant appendix/appendices, prior to being taken off the study, unless the reason for premature study discontinuation was that they did not start investigational agent or placebo.

6.3 Instructions for Evaluations

Sites must follow PPD source document guidelines.

All evaluations below are for both Phase II and III unless otherwise noted.

All stated evaluations are to be recorded on the eCRF unless otherwise specified. Refer to [section 7.0](#) for information on reporting of adverse events.

In the event of hospitalization, targeted physical examination, study diary entry and review, and specimen collection do not need to be completed during hospitalization but should be restarted after discharge. Other evaluations should be performed as feasible, including ascertainment of interventions, including medications received, and outcomes of interest/study endpoints.

Location of Study Visits

Sites should, in discussion with participants, determine the most appropriate place to conduct study visits, whether in-person or remote.

In person visits will take place at the clinic, at the participant's home, or at another non-clinic location if the site is able to accomplish all of the scheduled study visit evaluations.

Remote visits can take place over the phone or via telemedicine systems approved for use at the site.

6.3.1 Documentation of SARS-CoV-2 Infection

[Section 4.1.1.3](#) specifies assay requirements for SARS-CoV-2 infection documentation. SARS-CoV-2 infection documentation is recorded on the eCRF. If a viral load level is available, it should be recorded as well.

See the MOP for further guidance.

6.3.2 COVID-19 Symptoms

COVID-19 Symptom Screen

Participants will be asked about their first symptoms related to COVID-19 and their current symptoms.

The time from symptom onset at anticipated study entry (≤ 5 days versus > 5 days) should be recorded.

Post-Acute COVID-19 Assessment

Participants will be asked about potential COVID-19-related symptoms and diagnoses experienced after Day 28 using standardized questionnaires (see MOP for additional information).

6.3.3 Medical History

At Screening and updated at Study Entry, a complete medical history for the preceding 120 days should be recorded. Additionally, the following diagnoses should be recorded regardless of when the diagnosis was made, except where noted:

- autoimmune disease
- pulmonary embolus
- deep venous thrombosis
- HIV infection
- cancer (exclusive of basal/squamous cell skin cancer)
- acute viral respiratory infection (influenza, parainfluenza, respiratory syncytial virus, rhinovirus) within the previous 14 days (if known by participant)
- chronic lung disease
- asthma requiring daily inhaled medication
- obesity (body mass index [BMI] > 35 ; may be based on self-report of height and weight)
- hypertension
- cardiovascular disease
- diabetes
- chronic kidney disease
- history of cirrhosis
- exogenous or endogenous immunosuppression

The participant's risk category for COVID-19 progression ("higher" vs. "lower" risk) should be recorded. If participant meets the criteria for "higher" risk, all high risk criteria that are met should be recorded.

Any allergies to any medications and their formulations must also be documented.

See appendix/appendices for additional elements of the medical history that should be recorded.

6.3.4 Medication History

A medication history must be present, including start and stop dates. The table below lists the medications that must be included in the history at screening and updated at entry.

Table 6.3.4-1: Medication History

Medication/Category	Timeframe
All prescription drugs	Last 7 days
Corticosteroids, anabolic steroids	Last 30 days
Prescription drugs for high blood pressure	Last 3 months
Prescription drugs for diabetes and pre-diabetes	Last 3 months
Prescription drugs for lung disease	Last 3 months
Prescription drugs for heart disease	Last 3 months
Prescription drugs for autoimmune disease	Last 3 months
Cancer chemotherapy	Last 3 months
Antiretroviral therapy	Last 3 months
Immune-based therapy	Last 3 months
Blinded investigational agent	Last 12 months
CoV-related vaccines or treatments	Complete history
Hydroxychloroquine	Complete history
Antibiotics	Last 3 months
Anti-parasitics	Last 3 months
Alternative therapies	Last 3 months
Dietary supplements (including zinc and vitamins C and D)	Last 3 months

6.3.5 Smoking Status

A Smoking Status questionnaire will be completed as part of medical history and recorded on the eCRF.

6.3.6 Clinical Assessments

Physical Examination

Weight is measured only at screening.

At entry, perform physical exam, including cardiac exam, pulmonary exam, and vital signs (temperature, pulse, blood pressure, and resting peripheral oxygen saturation).

After entry, perform a targeted physical examination at the following visits: Phase II Day 3, Day 7, Day 14, Day 28, Week 24, and Premature Study D/C (before or after Day 28) and Phase III Day 28, Week 24, and Premature Study D/C (before or after Day 28). A targeted physical examination will also be performed at other visits not listed here if required for specific agents (see appendix/appendices). A targeted physical examination includes vital signs (temperature, pulse, blood pressure, and resting peripheral oxygen saturation) and examinations driven by any previously identified or new adverse event/targeted condition that the participant has experienced.

Supplemental oxygen use will be recorded at each visit at which vital signs are recorded.

At study entry, if peripheral oxygen saturation is <92% on usual supplemental oxygen requirements, the participant should be referred for emergency department evaluation and should not initiate investigational product.

Post-entry, peripheral oxygenation saturation measures <96% should be reviewed by an investigator and referral for medical attention made at the discretion of the investigator.

See appendix/appendices for any additional elements needed for the targeted exam.

Post entry, see [section 8.3](#) for collection requirements for pregnancy.

Concomitant Medications

Post entry, the following new and discontinued concomitant medications must be recorded:

- high blood pressure medications
- steroids or other immunosuppressive or immunomodulatory medication
- non-steroidal anti-inflammatory drugs (NSAIDs)
- chemotherapy
- antibiotics, antifungals, antiparasitics, and antivirals (including antiretrovirals)
- anticoagulants
- antiplatelets

- any approved or investigational agent felt to have potential COVID-19 activity (including hydroxychloroquine, chloroquine, ivermectin, HIV protease inhibitors, and SARS-CoV-2 vaccines)
- inhalers
- medications for symptoms of COVID-19, including aspirin, ibuprofen, acetaminophen, zinc, dietary supplements, herbal remedies, decongestants, cough suppressants, and antihistamines.

Assessment for Adverse Events

Beginning at entry, participants will be assessed at every visit (remote or in-person) for any new signs or symptoms and the relationship to study treatment.

Investigational Agent Modifications

Post entry, record any initial dose of treatment, modification to treatment, treatment interruption, and permanent discontinuation of treatment, and the reason for the modification, interruption, or discontinuation.

6.3.7 Collect/Update Secondary Contacts

Sites will capture contact information for at least two individuals that the site can contact if the participant cannot be reached (e.g., spouse, friend, neighbor). Sites will also request health care provider contact information and hospital(s) that the participant is likely to go to if they get sick.

Contact information for secondary contacts or health care provider will not be recorded on any eCRF.

At study entry only, sites will record the participant's home address in site records (it will not be reported on an eCRF).

6.3.8 Vital Status Check

If a participant cannot be reached after two attempts 24 hours apart, then their listed secondary contact person(s) or health care provider will be contacted for a check of the participant's vital status and study endpoints. In addition, for participants who prematurely discontinue for reasons other than withdrawal of consent or non-initiation of investigational product, or at any time the site becomes aware of a potential hospitalization or death after the participant discontinued study, site personnel should attempt to obtain information on the vital status of the participant and study endpoints as outlined in the MOPs.

Vital status contacts and other reported information should be recorded on the eCRFs.

6.3.9 Investigational Agent Administered

See relevant appendix/appendices for dispensing/administration details.

6.3.10 Study Kit Dispensed

The kit will include:

- copy of informed consent
- information about the study
- instructions on study procedures
- pocket/wallet card with site staff contact information
- instructions on what to do if participants have worsening symptoms/become hospitalized
- swabs for self-collected anterior nasal swabs with storage and transport materials **(Phase III only)**
- study diary (see below)

6.3.11 Study Diary

Participant-Completed Study Diary

Participants will be asked to keep a log of symptoms, medications they are taking for COVID-19 symptoms, and major events such as urgent visit to an emergency room or clinic and hospitalization in their study diary. This log will be completed on paper or electronically, if appropriate electronic systems are available.

At study entry, participants will complete the study diary with site staff prior to initiating investigational agent/placebo. Participants will be asked to complete subsequent entries per the SOE. The diary should be completed at approximately the same time every day.

If the day 28 visit occurs on study day 28, then the day 28 study diary may be completed with the site staff during the day 28 visit, otherwise it should be completed by the participant on study day 28.

Study Diary Reminder and Staff Review of Study Diary

Participant will be contacted every day on days 1-28 and reminded to complete their study diary. This reminder may be by telephone, text message, email, or other method for which the participant provides permission. A direct response from the participant is not required.

The study diary will be reviewed by study staff in person or remotely with each participant according to the schedule in [Tables 6.1-1](#) and [6.1-2](#). If an appropriate electronic system is available, the participant's diary entries will automatically be captured in the eCRF. If such a system is not available, the study staff will record the participant's answers on the study diary eCRF. If the participant uses a paper

diary and it is feasible, prior to or during the remote study visits, sites will ask the participant to send images of each of their study diary entries to be reviewed at the next study contact. See MOPS for requirements for timely eCRF entry of diary data.

Participants who report worsening symptoms from any cause during the trial may be referred to their health care provider or closest emergency room. Such instances will be recorded at the time of the notification, and during follow-up to assess study endpoints, i.e., hospitalization or death.

Retrieval of Study Diary

If the participant uses a paper diary, the study diary should be collected following the current Diary Completion Guidelines on the A5401 PSWP. See MOPS for additional instructions on retrieval of Study Diary.

6.3.12 Household Infection and Linkage Report

At Study Entry/Day 0, participants will be asked if anyone who resides in their household, defined as sharing indoor living space or housekeeping space (i.e., kitchen, dining area, or bathroom) has been diagnosed with SARS-CoV-2 infection or are also enrolled in the study, and the response recorded on the eCRF. If a household member is enrolled in the study, the participant ID for the first household member enrolled into the study will be recorded.

Post entry, participants will be asked if any new household members have been diagnosed with SARS-CoV-2 infection, and the response recorded on the eCRF.

6.3.13 Virologic Studies

Anterior nasal (**Phase III only**) and NP swabs (**Phase II only**) will be collected for quantitative SARS-CoV-2 RNA, performed in near real-time.

Influenza and other respiratory viral testing may be performed on stored NP swabs.

Additional information can be found in the MOP and the LPC.

Self-Collected Anterior Nasal Swabs (Phase III)

Participants will self-collect anterior nasal swabs. Participants will be instructed by study staff and will obtain the day 0 swab while observed by study staff. This swab should be collected prior to the first dose of investigational agent.

After Day 0, in phase III, nasal swabs will be self-collected by the participant on their own. Remote-collected nasal swabs will be stored at home as per the MOP.

Retrieval of Self-Collected Nasal Swabs (Phase III)

Site staff will retrieve the nasal swabs collected by the participants at home as per the MOP and LPC. The swabs will be processed, stored, and shipped to the central laboratory as per the LPC.

Staff-Collected NP Swab (Phase II only)

NP swabs will be collected during in-person visits. At study entry, the sample should be collected prior to the first dose of investigational agent.

6.3.14 Laboratory Evaluations

The following laboratory evaluations are for all investigational agents. If additional measures are needed, these are detailed in the relevant investigational agent appendix.

Refer to the LPC for details of collection, processing, and shipping. At screening, entry, and post-entry, all laboratory values must be recorded unless otherwise specified in the relevant appendix/appendices.

At study entry, blood samples should be collected prior to initiation of the investigational agent.

Blood can be collected outside of a clinic setting (e.g., home).

Inflammatory Markers

Lactate dehydrogenase, C-reactive protein, ferritin, and D-dimer will be performed.

Coagulation Markers

PT, PTT, INR, and fibrinogen will be performed.

Hematology

See relevant appendix/appendices for testing requirements.

Chemistry

See relevant appendix/appendices for testing requirements.

Pregnancy Testing

See relevant appendix/appendices for testing requirements.

6.3.15 Pharmacokinetics

Pharmacokinetic sampling will be performed per the relevant appendix/appendices.

6.3.16 Stored Samples

Collected plasma, sera, or PBMC will be used to assess SARS-CoV-2 virologic and immune responses. All Entry/Day 0 samples should be collected prior to the first dose of investigational agent/placebo. Additional samples will be collected for agent-specific evaluations per the relevant appendix/appendices.

Stored Plasma

Blood plasma will be collected and stored for future testing, including:

- immunologic studies including markers linked to systemic inflammation (IL-6, TNF-a), inflammasome activation (IL-1beta, IL-18), interferon pathways (IP-10, type I interferon), neutrophil activation (MPO), monocyte activation (sCD14), as well as markers associated with coagulation or endothelial cell dysfunction (VWF, P-selectin, tissue factor)
- SARS-CoV-2 seroconversion and antibody titers (among seroconverters)
- **Quantitative SARS-CoV-2 RNA**
- full viral genome sequencing will be performed from select samples that are detectable for SARS-CoV-2 RNA to assess for signs of viral evolution and resistance to the investigational agent or immune responses. If sequence analysis suggests viral escape from the investigational agent (e.g. mutations in putative binding regions or epitopes), then phenotypic analyses may be pursued.

Stored Serum

Blood sera will be collected and stored for future testing, including:

- total and neutralizing antibody assays

Stored Peripheral Blood Mononuclear Cells (PBMCs)

PBMCs will be collected only at select sites. PBMC processing must be done in an IQA-approved lab. PBMCs will be stored for future testing, which may include the following:

- cellular immune responses between treatment and control samples, including assessment of T-cell responses to SARS-Cov-2 protein (phase II: days 0, 7, 28, and week 24)
- cellular activation/exhaustion phenotypes among innate or adaptive immune cells (phase II: days 0, 7, 28, and week 24)
- host genetics

7.0 ADVERSE EVENTS AND STUDY MONITORING

See relevant appendix/appendices for any modifications to recording of AEs and study monitoring.

See the MOPS for further instructions on AE reporting.

7.1 Definitions of Adverse Events

Adverse Event

An adverse event (AE) is any unfavorable and unintended sign (including an abnormal laboratory finding), symptom, or diagnosis that occurs in a study participant during the conduct of the study REGARDLESS of the attribution (i.e., relationship of event to medical treatment/investigational agent/device or procedure/intervention). This includes any occurrence that is new in onset or aggravated in severity or frequency from the baseline condition.

The scale used in the Study Diary for participant symptoms does NOT equate to the AE grading as found in the Division of AIDS Table for Grading the Severity of Adult and Pediatric Adverse Events (DAIDS AE Grading Table), corrected Version 2.1, July 2017.

Sites should grade participant symptoms as they normally would according to the DAIDS AE Grading Table.

Serious Adverse Events (SAEs)

An SAE is defined as any untoward medical occurrence that results in any of the following outcomes:

- results in death
- is life-threatening
- requires inpatient hospitalization or prolongation of existing hospitalization
- results in persistent or significant disability/incapacity
- is a congenital anomaly/birth defect.
- is an important medical event that may not be immediately life threatening or result in death or hospitalization but may jeopardize the participant or may require intervention to prevent one of the other outcomes listed in the definition above).

Adverse Events of Special Interest

An adverse event of special interest (AESI) (serious or nonserious) is defined as an AE or SAE of scientific and medical concern specific to the investigational agent, for which ongoing monitoring and rapid communication by the investigator to the sponsor could be appropriate.

See appendix/appendices for AESIs related to specific investigational agents.

Suspected Unexpected Adverse Events

A Suspected Unexpected Serious Adverse Reaction (SUSAR) is defined as a serious adverse reaction, the nature or severity of which is not consistent with the applicable product information (e.g., Investigator's Brochure for an unapproved investigational product).

7.2 Eliciting and Documenting Adverse Events

Adverse events will be assessed beginning at Entry/Day 0 and through study completion or discontinuation.

If the investigator learns of any SAE, including a death, at any time after a participant has been discharged from the study, and he/she considers the event to be reasonably related to the investigational agent or study participation, the investigator must promptly notify the sponsor.

Serious AEs that occur after study completion or discontinuation need not be reported unless the investigator considers them related to the investigational product.

At every study visit, participants will be asked a standard nonleading question to elicit any medically related changes in their well-being. They will also be asked if they have been hospitalized, had any accidents, used any new medications, or changed concomitant medication regimens (both prescription and OTC medications).

In addition to participant observations, AEs identified from any study data (e.g., laboratory values, physical examination findings, or identified from review of other documents [e.g., participant diaries]) that are relevant to participant safety will be documented on the AE page in the eCRF.

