1.0 STUDY OBJECTIVES

1.1 Co-Primary Objectives

- 1.1.1 Phases II and III: To evaluate safety of the investigational agent.
- 1.1.2 Phase II: To determine efficacy of the investigational agent to reduce the duration of COVID-19 symptoms through study day 28.
- 1.1.3 Phase II: To determine the efficacy of the investigational agent to increase the proportion of participants with nasopharyngeal (NP) SARS-CoV-2 RNA below the lower limit of quantification (LLoQ) at study days 3, 7, 14, and 28.
- 1.1.4 Phase III: To determine if the investigational agent will prevent the composite endpoint of either hospitalization or death through study day 28. Hospitalization is defined as ≥ 24 hours of acute care, in a hospital or similar acute care facility, including Emergency Rooms or temporary facilities instituted to address medical needs of those with severe COVID-19 during the COVID-19 pandemic.

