9.2 Premature Study Discontinuation

- Failure to initiate investigational agent.
- Request by the participant to withdraw consent.
- Request of the health care provider if they think the study is no longer in the best interest of the participant.
- At the discretion of the IRB/EC, FDA, NIAID, ACTG, Office for Human Research Protections (OHRP), other government agencies as part of their duties, investigator, or industry supporter.
- Any additional indications are outlined in the relevant appendix/appendices.

In the event that a participant prematurely discontinues from the study, unless they have withdrawn consent or never initiated investigational agent/placebo, sites will attempt to obtain information regarding vital status (including date last seen alive, hospitalization, date of death, and primary cause of death) from other sources (e.g., family members, other designated secondary contacts, or clinic records). See the MOP for further guidance.

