10.2.2 Phase III: Primary Outcome Measures

10.2.2.1 Efficacy: Death from any cause or hospitalization during the 28-day period from and including the day of the first dose of investigational agent or placebo. Hospitalization is defined as \geq 24 hours of acute care, in a hospital or similar acute care facility, including Emergency

Rooms or temporary facilities instituted to address medical needs of those with severe COVID-19 during the COVID-19 pandemic.

10.2.2.2 Safety: New Grade 3 or higher AE through 28 days.

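### AE reporting stops at early exit and becomes related-only, so a known hospitalization or death before day 28 can count for efficacy yet may be absent from the all-cause co-primary safety outcome

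*Protocol*

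**What the plan says.** Safety is a co-primary objective in section 1.1: "Phases II and III: To evaluate safety of the investigational agent". The phase III outcome in 10.2.2.2 is "Safety: New Grade 3 or higher AE through 28 days", and 10.2.1.3 is the same for phase II. Sections 10.6.1 and 10.6.2 analyse it as a proportion by day 28. Neither the outcome nor the analysis mentions relatedness or a cut-off at study exit. Section 7.1 defines an adverse event as one that "occurs in a study participant during the conduct of the study REGARDLESS of the attribution".

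Section 7.2 sets the collection window: "Adverse events will be assessed beginning at Entry/Day 0 and through study completion or discontinuation". After exit, "Serious AEs that occur after study completion or discontinuation need not be reported unless the investigator considers them related to the investigational product". Completion and early discontinuation are treated alike, so leaving on day 5 has the same consequence as finishing at week 24.

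For the clinical endpoint, collection continues after exit. Section 9.2 says that, unless consent was withdrawn or treatment never started, "sites will attempt to obtain information regarding vital status (including date last seen alive, hospitalization, date of death, and primary cause of death". Section 6.3.8 gives a matching instruction and extends it to any time a site hears of a possible hospitalization or death after exit. The phase III primary efficacy outcome is "Death from any cause or hospitalization during the 28-day period from and including the day of the first dose", and 10.6.2 censors leavers only when their later outcome cannot be ascertained.

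**The concern.** The collection rule and the outcome do not match. The outcome is all-cause over a fixed 28 days. For anyone who leaves before day 28, the serious-event rule becomes related-only on the day of exit. The same protocol asks the site to find out whether that person was hospitalized or died, and uses the answer for efficacy.

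At stake is the integrity of a co-primary outcome. Its hospitalization and death component could disagree with the efficacy data on the same people, and the gap falls among early leavers, who may differ from those who stay. An attribution judgement would also have entered a comparison meant to be free of one.

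**Working it through.** **Following one participant through the rules.** Suppose a treated participant leaves on day 5 at a health care provider's request (a reason listed in 9.2), does not withdraw consent, and is admitted with COVID-19 on day 12 for more than 24 hours.

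1. Sections 6.3.8 and 9.2: the site should look for this event and record it on the eCRFs. No transfer to the AE page is stated.
2. Sections 10.2.2.1 and 10.6.2: once known, it is a phase III primary efficacy event on day 12.
3. Section 7.2: AE assessment ended on day 5. Inpatient admission is serious under 7.1 ("requires inpatient hospitalization or prolongation of existing hospitalization"), but the site is released from reporting it unless it is judged related.
4. Section 7.2.2: a related event is one that other conditions, including disease progression, do not seem to explain. A COVID-19 admission would seldom qualify.
5. Section 7.2.1: grading is required for AEs that are reported. An event never entered as an AE need not carry the grade on which 10.2.2.2 depends.

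Had the same admission occurred on day 4, it would have been reportable whatever its cause; section 7.3 expressly includes disease progression.

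**Who is affected.** Participants who never start treatment are outside the analysis set (10.6). Those who stop treatment but stay on study are still fully assessed (6.2.5). Those who withdraw consent are outside the routine search. There remain people taken off study for the other 9.2 or appendix reasons, and people who became unreachable and were later traced.

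**Size.** The protocol's expected event count reproduces: 421 × (0.15 + 0.075) = 94.7, the 95 stated in 10.5.2. The 5% in 10.4.2 is loss to follow-up before an event, and the 10% in 10.5.2 is a loss-to-follow-up benchmark. Both describe outcomes that are unknown. The quantity needed is the fraction f who leave before day 28 with the later outcome known. Also needed are the share s of 28-day risk still ahead at exit and the share u of those events judged unrelated and not otherwise entered:

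missing events, both arms = 421 × f × s × u × 0.225

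The protocol gives none of f, s or u. Purely as an assumption, set s = u = 1 and let leavers carry average risk. Each 1% of f is then 421 × 0.01 × 0.225 = 0.95 events, or 1% of 94.7. Over an assumed range with u = 1:
- f = 2%, s = 0.5: 421 × 0.02 × 0.5 × 0.225 = 0.95 events
- f = 10%, s = 1: 421 × 0.10 × 0.225 = 9.5 events

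If f, s and u are equal in the two arms, both proportions shrink by the same factor and their ratio is unchanged. At the upper end, 15% and 7.5% become 13.5% and 6.75%. These figures show scale only. They are not estimates from the protocol, and sicker leavers would raise them.

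**The case against.** The case for leaving the text alone is that little can go wrong. The exemption is permissive, and a site may still report. Section 7.2 also sends AEs found in any study data to the AE page when they bear on participant safety, and section 7.0 refers to the manual of procedures and the appendices, which may say more. AEs are assessed up to exit, so the event that prompted leaving is in scope. Deaths and hospitalizations remain in an all-cause randomized comparison, primary in phase III and secondary in phase II. In phase III the DSMB sees them by arm (10.5.2).

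Most of this stands, and it rules out three stronger readings that a reader might infer:
- That the events are lost, or that leavers are analysed as AE-free. The rule only allows omission, and no section says how leavers enter the safety analysis.
- That 5% or 10% loss gives a count of missed events. Those figures describe unknown outcomes, and a leaver traced to an admission or death is not one of them.
- That harm is hidden from the trial. The event may be missing from one outcome but remains visible in another.

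The objection does not remove the mismatch. The general sentence on AEs found in study data does not mention vital status information or lift the specific exemption, so sites may act differently. This is a collection rule: an analysis plan cannot supply a grade that was never recorded.

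**Conclusion.** The point holds as an internal inconsistency that can be corrected. Section 7.2 allows a known hospitalization or death before day 28 to stay out of a safety outcome defined as all-cause through day 28, while 6.3.8, 9.2 and 10.6.2 bring the same event into the efficacy outcome.

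The size cannot be derived from the document. It is probably small, because the exits that qualify are few in kind. No sample size, power or efficacy figure is affected.

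The conclusion assumes that these hospitalizations and deaths would usually be Grade 3 or higher; the grading table is not in the document. It also assumes that the manual and appendices, not seen here, do not already override the exemption.

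**What to change.** Add to 7.2: for treated participants who leave before day 28 without withdrawing consent, any death, hospitalization or other serious event that the site learns of with onset through day 28 is entered and graded on the AE eCRF regardless of attribution. It counts in 10.2.1.3 or 10.2.2.2 if Grade 3 or higher. Keep the related-only rule for events after day 28. Name hospitalization explicitly, because the efficacy definition accepts 24 hours or more in an emergency room, which need not be the inpatient stay in the SAE definition. Cross-refer from 6.3.8 and 9.2.

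The cost is a few extra AE forms, using information that sites already seek. Some will be graded and attributed from second-hand sources such as family members or clinic records. Non-serious Grade 3 events in leavers would still be incompletely captured, so the outcome would remain less complete for them than for those who stay.
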